## 13.6 Vital signs and weight measurements

Vital sign measurements (systolic blood pressure, diastolic blood pressure, heart rate [HR], respiratory rate [RR], body temperature [°C]), and weight will be obtained at the visits designated in the schedule of visits and procedures (Table 4). Height will be measured at the screening visit only. Blood pressure, HR, and RR will be obtained after subjects have been resting for 5 minutes. For subjects with an elevated BP ( $\geq$  140/90 mmHg), confirmation should be obtained by performing 3 measurements (at least 5 minutes apart) to yield a mean value. Systolic BP  $\geq$  140 mmHg or diastolic BP  $\geq$  90 mmHg should be confirmed by repeat measurements after an hour.

## 13.7 Electrocardiograms

Electrocardiograms will be complete, standardized, 12-lead recordings that permit all 12 leads to be displayed on a single page with an accompanying lead II rhythm strip below the customary 3 x 4 lead format. In addition to a rhythm strip, a minimum of 3 full complexes should be recorded from each lead simultaneously. Subjects should be in the recumbent position for a period of 5 minutes prior to the ECG. An ECG abnormality may meet the criteria as an AE as described in this protocol (Section 15) and the CRF instructions. In case of basal ECG abnormality but does not involve any risk to the patient by the judgment of the investigator, the patient may be included in the study and need not be repeated ECG otherwise indicated by the investigator.

In these instances, the AE corresponding to the ECG abnormality will be recorded on the Adverse Events CRF. For ECG abnormalities meeting criteria as SAEs (Section 14.3), the study site must fax the SAE report including the ECG report to the number indicated in the Investigator File using the SAE reporting form.

#### 13.8 Echocardiograms

An echocardiogram to assess left ventricular ejection fraction (LVEF) will be performed during the screening phase and every 6 months following the first dose of study drug while the subject is on treatment or sooner, if clinically indicated. Echocardiograms should be performed following the local protocol to assess LVEF. LVEFs as assessed by the institution will be entered onto the eCRF. Investigator assessment will be based upon institutional reports.

Page 58 of 88 Date: April 04th, 2016

#### 14. Adverse events

An adverse event is any untoward medical occurrence in a subject or clinical investigation subject administered an investigational product. An AE does not necessarily have a causal relationship with the study drug. For this study, the study drug is lenvatinib. The criteria for identifying adverse events are:

- Any unfavorable and unintended sign (including an abnormal laboratory finding), symptom, or disease temporally associated with the use of a medicinal product, whether or not considered related to the medicinal product.
- Any new disease or exacerbation of an existing disease.
- Any deterioration in non-protocol-required measurements of a laboratory value or other clinical test (e.g., ECG or x-ray) that results in symptoms, a change in treatment, or discontinuation from study drug.
- Recurrence of an intermittent medical condition (e.g., headache) not present at baseline.

#### Reporting Laboratory abnormalities

An abnormal laboratory test result may be considered as an adverse event if the identified laboratory abnormality leads to any type of intervention whether prescribed in the protocol or not.

### A laboratory result should be considered by the investigator to be an adverse event if it:

- Results in the withdrawal of study treatment.
- Results in withholding of study treatment pending some investigational outcome.
- Upon medical evaluation, results in the initiation of an intervention (e.g., potassium supplement for hypokalemia).
- Is an out-of-range laboratory value that, in the investigator's judgment, fulfills the definition of an AE with regard to the subject's medical profile.
- Increases in severity compared to baseline by ≥ 2 CTCAE grades (see Appendix IV for CTCAE v4.03), with the exception of lymphocytes, albumin, cholesterol, glucose, and phosphate. For these tests, a change of ≥ 2 grades will be evaluated by the investigator to determine if they are of clinical significance and, if so, will be considered an adverse event.

Abnormal laboratory values should not be listed as separate AEs if they are considered to be part of the clinical syndrome that is being reported as an AE. Any laboratory abnormality considered to constitute an adverse event should be reported on the Adverse Event CRF.

It is the responsibility of the investigator to review all laboratory findings in all subjects and determine if they constitute an AE. Medical and scientific judgment should be exercised in deciding whether an isolated laboratory abnormality should be classified as an adverse event.

Regarding the Laboratory abnormalities only should be notified as SAE those abnormalities that meet Grade 3 or above following the CTCAE criteria (v.4.03), taking into account the following situations:

- Laboratory abnormality is within normal limits at baseline and has increased in severity to meet CTCAE (v4.03) criteria of Grade 3 or above and it is considered by the investigator to meet serious criteria should be reported as SAE. i.e. laboratory abnormality is within normal limits at baseline and has increased in severity to meet CTCAE (v4.03) criteria of Grade 3 or above and it is not considered by the investigator to meet serious criteria should not be reported as SAE.
- Laboratory abnormality is outside normal limits at baseline and increases in severity to CTCAE
   (v4.03) Grade 4 or above. These abnormalities are automatically considered to be serious and
   should be reported as SAE.
- Significant laboratory abnormalities should not be listed as separate AEs or SAEs if they are considered to be part of the clinical syndrome that is being reported as an AE or SAE.

An abnormal ECG result, if not otherwise considered part of a clinical symptom that is being reported as an AE, should be considered an AE if either there is worsening by  $\geq$  2 CTCAE v4.03 grade levels from baseline or a QTc increase of  $\geq$ 60 msec from baseline. Any ECG abnormality that the investigator considers to be an adverse event should be reported as such. In case of basal ECG abnormality but does not involve any risk to the patient by the judgment of the investigator, the patient may be included in the study and need not be repeated ECG otherwise indicated by the investigator.

Adverse events in clinical investigation subjects include any change in the subject's condition. This includes symptoms, physical findings, or clinical syndromes. All AEs encountered during the clinical study will be reported on the CRF. All AEs, regardless of relationship to study drug or procedure, should be collected beginning from the time the subject signs the study consent through the last visit and for 28 days following study drug discontinuation.

Progression of malignant disease should not be recorded as an adverse event in studies where it is included as an endpoint for underlying disease. If the progression leads to an untoward medical occurrence (increased pain, pleural effusion, etc.), then this medical occurrence should be the adverse event.

All AEs must be followed until resolution or for 28 days after the subject's last study visit, whichever comes first.

Every effort must be made by the investigator to categorize each AE according to its severity and its relationship to the study treatment.

Page 60 of 88 Date: April 04th, 2016

## 14.1 Assessing severity of adverse events

AEs will be graded on a 5-point scale according to CTCAE v4.03 (Appendix IV) as follows:

- Grade 1 = Mild: asymptomatic or mild symptoms; clinical or diagnostic observations only; intervention not indicated.
- Grade 2 = Moderate: minimal, local, or noninvasive intervention indicated; limiting ageappropriate instrumental activities of daily living (ADL).
- Grade 3 = Severe or medically significant but not immediately life-threatening: hospitalization or prolongation of hospitalization indicated; disabling; limiting self-care ADL.
- Grade 4 = Life-threatening consequences: urgent intervention indicated.
- Grade 5 = Death related to AE.

Investigators will collect all CTCAE grades (Appendix IV) for AEs (for both increasing and decreasing severity). All adverse events reported using CTCAE classification and graded as 4 or 5 are to be considered serious. The criteria for assessing severity are different from those used for seriousness (see Serious Adverse Events and Other Events of Interest).

## 14.2 Assessing relationship to study treatment

Items to be considered when assessing the relationship of an AE to the study treatment are:

- Temporal relationship of the onset of the event to the initiation of the study treatment.
- The course of the event, considering especially the effect of discontinuation of study treatment or reintroduction of study treatment, as applicable.
- Whether the event is known to be associated with the study treatment or with other similar treatments.
- The presence of risk factors in the study subject known to increase the occurrence of the event.
- The presence of non-study treatment-related factors which are known to be associated with the occurrence of the event.

#### Classification of causality

- Not Related: A causal relationship between the study treatment and the AE is not a reasonable possibility.
- Related: A causal relationship between the study treatment and the AE is a reasonable possibility. The investigator must further qualify the degree of certainty as "possible" or "probable."

#### 14.3 Serious adverse events and other events of interest

A serious adverse event is any untoward medical occurrence that at any dose:

Page 61 of 88 Date: April 04th, 2016

- Results in death;
- Is life-threatening (i.e., the subject was at immediate risk of death from the adverse event as it occurred; this does not include an event that, had it occurred in a more severe form or was allowed to continue, might have caused death);
- Requires inpatient hospitalization or prolongation of existing hospitalization;
- Results in persistent or significant disability/incapacity; or
- Is a congenital anomaly/birth defect (in the child of a subject who was exposed to the study drug).
- Other important medical events that may not be immediately life-threatening or result in death or hospitalization, but when based on appropriate medical judgment, may jeopardize the subject or may require intervention to prevent one of the outcomes in the definition of SAE listed above should also be considered serious adverse events. Medical and scientific judgment should be exercised in deciding whether expedited reporting is appropriate in such situations.

In addition to the above, other events of interest which include pregnancy and overdose. All events of these types are to be reported on the eCRF whether or not they meet the criteria for an SAE.

The following hospitalizations are not considered to be SAEs because there is no "adverse event" (i.e., there is no untoward medical occurrence) associated with the hospitalization:

- Hospitalizations for respite care;
- Planned hospitalizations required by the protocol;
- Hospitalization planned prior to informed consent (where the condition requiring the hospitalization has not changed post study drug administration);
- Hospitalization for administration of study drug or insertion of access for administration of study drug.

### 14.4 Reporting Laboratory abnormalities

An abnormal laboratory test result may be considered as an adverse event if the identified laboratory abnormality leads to any type of intervention whether prescribed in the protocol or not.

#### A laboratory result should be considered by the investigator to be an adverse event if it:

- Results in the withdrawal of study treatment.
- Results in withholding of study treatment pending some investigational outcome.
- Upon medical evaluation, results in the initiation of an intervention (e.g., potassium supplement for hypokalemia).
- Is an out-of-range laboratory value that, in the investigator's judgment, fulfills the definition of an AE with regard to the subject's medical profile.

Page 62 of 88 Date: April 04th, 2016

• Increases in severity compared to baseline by ≥ 2 CTCAE grades (see Appendix IV for CTCAE v4.03), with the exception of lymphocytes, albumin, cholesterol, glucose, and phosphate. For these tests, a change of ≥ 2 grades will be evaluated by the investigator to determine if they are of clinical significance and, if so, will be considered an adverse event.

Abnormal laboratory values should not be listed as separate AEs if they are considered to be part of the clinical syndrome that is being reported as an AE. Any laboratory abnormality considered to constitute an adverse event should be reported on the Adverse Event CRF.

It is the responsibility of the investigator to review all laboratory findings in all subjects and determine if they constitute an AE. Medical and scientific judgment should be exercised in deciding whether an isolated laboratory abnormality should be classified as an adverse event.

## 14.4.1 Laboratory abnormality to be considered as SAE

Regarding the Laboratory abnormalities only should be notified as SAE those abnormalities that meet Grade 3 or above following the CTCAE criteria (v.4.03), taking into account the following situations:

- Laboratory abnormality is within normal limits at baseline and has increased in severity to meet CTCAE (v4.03) criteria of Grade 3 or above and it is considered by the investigator to meet serious criteria should be reported as SAE. i.e. laboratory abnormality is within normal limits at baseline and has increased in severity to meet CTCAE (v4.03) criteria of Grade 3 or above and it is not considered by the investigator to meet serious criteria should not be reported as SAE.
- Laboratory abnormality is outside normal limits at baseline and increases in severity to CTCAE
   (v4.03) Grade 4 or above. These abnormalities are automatically considered to be serious and
   should be reported as SAE.

Significant laboratory abnormalities should not be listed as separate AEs or SAEs if they are considered to be part of the clinical syndrome that is being reported as an AE or SAE.

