- b) Gastrointestinal origin: progression after therapy with antitumoral doses of somatostatin analogs (octreotide LAR 30 mg every 28 days or Lanreotide 120 mg every 28 days) and/or interferon treatment.
- 5. Only for patients with pancreatic origin neuroendocrine tumors, one previous line with chemotherapy is allowed.
- 6. Concomitant somatostatin analogues are allowed in both cohorts during the study.
- 7. Patients with known brain metastases who have completed whole brain radiotherapy, stereotactic radiosurgery or complete surgical resection, will be eligible if they have remained clinically stable, asymptomatic and off of steroids for at least one month.
- 8. All prior chemotherapy or radiation-related toxicities must have resolved to < Grade 2 (following CTCAE V 4.03 grade levels), except alopecia and infertility.
- 9. Subjects must have an Eastern Cooperative Oncology Group (ECOG) Performance Status of 0 1 (Appendix II).
- 10. Previous liver locoregional therapies, such as (chemo) embolization, radiofrequency or liver-directed radioembolization, or systemic peptide-receptor radionucleotide therapy are allowed if the procedure was performed at least 6 months previous the informed consent form signature.
- 11. Adequately controlled blood pressure with or without antihypertensive medications, defined as BP < 150/90 mmHg at screening and no change in antihypertensive medications within 1 week prior to the Screening Visit.
- 12. Adequate renal function defined as calculated creatinine clearance ≥ 30 mL/min per the Cockcroft and Gault formula (Appendix III).

EudraCT no.: 2015-001467-39

Page 28 of 88 Date: April 04th, 2016

- 13. Adequate bone marrow function, defined as:
  - a) Absolute neutrophil count (ANC)  $\geq$  1500/mm3 ( $\geq$  1.5 × 10^3/µL).
  - b) Platelets ≥ 100,000/mm3 (≥ 100 × 109/L).
  - c) Hemoglobin ≥ 9.0 g/dL.
- 14. Adequate blood coagulation function as evidenced by an International Normalized Ratio (INR) ≤ 1.5. Prophylactic low molecular weight heparin therapy is allowed.
- 15. Adequate liver function:
  - a) Bilirubin ≤ 1.5 × the upper limit of normal (ULN) except for unconjugated hyperbilirubinemia or Gilbert's syndrome.
  - b) Alkalin phosphatase, alanine aminotransferase (ALT), and aspartate aminotransferase (AST) ≤ 3 × the ULN (≤ 5 × ULN if subject has liver metastases).
- 16. Males or females age ≥ 18 years at the time of informed consent.

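### Section 14.4.1 ties SAE notification of laboratory abnormalities to grade and baseline value, which contradicts the outcome-based SAE definition in 14.3 and the duty to report every SAE in 14.5.1

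*Protocol*

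**What the plan says.** Protocol section 14.4.1 opens with a limit on what may be notified. Of laboratory abnormalities it says that "only should be notified as SAE those abnormalities that meet Grade 3 or above", graded by CTCAE v4.03. It then lists two situations.

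- Normal baseline: "Laboratory abnormality is within normal limits at baseline and has increased in severity to meet CTCAE (v4.03) criteria of Grade 3 or above". The event is an SAE if the investigator also judges that serious criteria are met, and is expressly not to be reported as one if they are not.
- Out-of-range baseline: "Laboratory abnormality is outside normal limits at baseline and increases in severity to CTCAE" "Grade 4 or above. These abnormalities are automatically considered to be serious and" are to be reported as SAEs. Grade 3 is not mentioned here.

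The same text stands in the laboratory part of the opening of Section 14.

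Three other sections bear on the point. Section 14.3 defines an SAE by its outcome, for example "Requires inpatient hospitalization or prolongation of existing hospitalization", and also includes important medical events; it sets no minimum grade and no baseline condition. Section 14.1 says "The criteria for assessing severity are different from those used for seriousness". Section 14.5.1 requires all SAEs, related or not, to be reported within 24 hours of awareness.

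**The concern.** Section 14.4.1 uses severity and the baseline value to decide what is notified as serious, although 14.1 keeps severity and seriousness apart and 14.3 defines seriousness by outcome alone. The result is also uneven. The same Grade 3 abnormality, with the same admission, has a listed SAE route if the patient entered with a normal value and none if the patient entered with an abnormal one.

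Abnormal entry values are allowed by design. Section 8.1 admits alkaline phosphatase, ALT and AST up to 3 × ULN ("≤ 5 × ULN if subject has liver metastases"), bilirubin up to 1.5 × ULN, and hemoglobin down to 9.0 g/dL. The out-of-range branch of 14.4.1 is therefore an ordinary case in this trial.

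Safety is a secondary objective, which SAP section 4.2 assesses by AEs and SAEs. Protocol 20.10 plans an overview that includes SAEs and separate tables of treatment-emergent SAEs. Sections 14.6 and 14.7 make expedited and SUSAR reporting depend on complete SAE information from the sites. A serious event that is not classified as an SAE is missing from all of these.

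**Working it through.** No arithmetic applies. The check sets the rules side by side for one test case: an isolated laboratory abnormality that leads to inpatient admission, so that a 14.3 criterion is met.

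| Baseline value | CTCAE grade reached | Under 14.4.1 | Under 14.3 with 14.5.1 | Same result? |
|---|---|---|---|---|
| Normal | Below 3 | Not notified as SAE | SAE, 24 hours | No |
| Normal | 3 | SAE if investigator judges serious criteria met | SAE, 24 hours | Yes |
| Normal | 4 or above | SAE if investigator judges serious criteria met | SAE, 24 hours | Yes |
| Out of range | Below 3 | Not notified as SAE | SAE, 24 hours | No |
| Out of range | 3 | No route listed | SAE, 24 hours | No |
| Out of range | 4 or above | SAE automatically | SAE, 24 hours | Yes |

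Three of the six cells conflict: both cells below Grade 3, and Grade 3 from an out-of-range baseline. (A different conflict, not counted here, concerns Grade 4 from a normal baseline: 14.1 makes every Grade 4 or 5 AE serious, while 14.4.1 leaves this case to the investigator.)

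The next question is whether other text closes the three cells.

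1. **Precedence.** No passage says whether 14.4.1 or 14.3 governs. By its title, 14.4.1 is the section a site would look up for a laboratory event.
2. **Section 13.5.** It requires an SAE report for laboratory abnormalities that meet SAE criteria, but refers the reader to Section 15.3 for those criteria. Section 15.3 is Database Quality Assurance, so the pointer does not lead to 14.3.
3. **Clinical-syndrome rule.** Section 14.4.1 says that a laboratory value forming part of a reported syndrome is not listed separately. A patient admitted with such a syndrome has the syndrome as the SAE, and no laboratory grade limit applies. This covers many admissions but not an isolated abnormality, so the gap is confined to isolated abnormalities.
4. **AE recording.** Section 14.4 sends laboratory abnormalities that qualify as AEs to the AE CRF, and one route to qualifying is that the abnormality prompts an intervention. TEAEs are tabulated by grade and relatedness (20.10), and graded laboratory parameters by CTCAE grade (20.11). The event is not lost from the data; its serious classification can be.

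**The case against.** The strongest reply is that 14.3 and 14.5.1 remain in force, so a site reading the whole of Section 14 would report these events. This stands against the stronger reading that a reader might infer, namely that such events go unreported. The documents give two conflicting instructions; they do not uniformly suppress the cases. It does not remove the conflict, because the section specific to laboratory events gives a different answer from the general one and nothing ranks them.

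A second reply is that Grade 3 from an abnormal baseline is only omitted. The lead-in admits Grade 3 or above, and the second bullet can be read as an extra automatic trigger that leaves other Grade 3 events to 14.3. It is correct that this is an omission and not an express bar: unlike the first bullet, the second contains no instruction not to report. But the reading has to be supplied by the reader, and the first bullet spells out a Grade 3 route that the second lacks.

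A third reply is that the part below Grade 3 has few cases, because the general Grade 3 description in 14.1 and Appendix IV already covers events for which admission is indicated. This largely stands. It is not complete: Appendix IV says that each AE term has its own severity descriptions, so admission does not by itself set the grade, and the important-medical-event criterion in 14.3 needs no admission.

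A reader might also infer that the safety results are understated in the highest-risk patients. The eligibility limits show only that abnormal baselines are allowed. They do not show that these patients are at higher risk, and the AE and laboratory grade tables would still contain events that qualify as AEs.

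**Conclusion.** The inconsistency is real and should be corrected. As written, 14.4.1 and its duplicate conflict with 14.3 and 14.5.1, and sit badly with 14.1. A site that follows 14.4.1 can fail to classify and notify as SAEs:

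- isolated Grade 3 laboratory abnormalities from an out-of-range baseline that meet a 14.3 criterion, which is the main gap; and
- isolated abnormalities below Grade 3 that meet a 14.3 criterion, which are probably few.

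For these events, what is at risk is SAE status and what follows from it, not all recording. The conclusion assumes only that some sites apply 14.4.1 literally.

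The number affected cannot be estimated from the documents. A count would need the share of patients entering with an out-of-range value, the rate of isolated laboratory events that meet a 14.3 criterion, how many sites follow 14.4.1 over 14.3, and how many affected patients have another reported SAE. None of these is given. The finding rests on the text and needs no count.

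**What to change.** Amend 14.4.1 and its duplicate in the opening of Section 14 to agree with 14.3 and 14.5.1. Suggested wording: a laboratory abnormality that meets any criterion in Section 14.3 is reported as an SAE, whatever its CTCAE grade and whatever the baseline value. Remove the Grade 3 floor and the baseline-dependent Grade 4 condition as limits on reporting; grade rules may stay only as additional triggers. The clinical-syndrome rule can remain. In 13.5, replace the reference to Section 15.3 with one to the SAE definition in 14.3.

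The cost is a wording amendment, a memo to sites and slightly more SAE forms. Treatment, visits and sample size do not change.
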